3.2 NUMBER OF CENTERS

Approximately 50 study centers in the United States (US) and Canada will be eligible for participation in the current study. Additional study sites selected to participate in future studies may also be included.

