10.4.2 DISEASE RESPONSE ANALYSIS

The analysis of disease response will be based on the FAS populations defined in [Section 10.3.2](#). The assessment of disease response will be based on duration of OS, PFS, and TTP. For patients previously enrolled in PX-171-008, response may be first noted in PX-171-010. Durations will be calculated from the date of disease response documented in the subjects' prior carfilzomib protocol, or in PX-171-010 for subjects previously enrolled in PX-171-008, to the first documentation of the endpoint's occurrence in the extended trial.

Depending on the completeness of the available follow-up data, analysis of each endpoint will be performed based on the Kaplan-Meier method. The date of progression will be determined using the progression criteria described in [Appendix D–E](#). The date of censoring for subjects who end the study without documented progression will correspond to the date the last disease assessment was performed. Analysis will be performed separately by disease cohort (MM or solid tumor).

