APPENDIX D: INTERNATIONAL UNIFORM RESPONSE CRITERIA FOR MULTIPLE MYELOMA

Summary Table	
Response Subcategory	Response Criteria
sCR	CR as defined below plus normal FLC ratio and absence of clonal cells in bone marrow by immunohistochemistry or immunofluorescence. ¹
CR	Negative immunofixation on the serum and urine, disappearance of any soft tissue plasmacytomas, and < 5% plasma cells in bone marrow
VGPR	Serum and urine M-protein detectable by immunofixation but not on electrophoresis or 90% or greater reduction in serum M-protein with urine M-protein level < 100 mg per 24 hours
PR	
≥ 50% reduction of serum M-protein and reduction in 24 hour urinary M-protein by ≥ 90% or to < 200 mg per 24 hours
 
If the serum and urine M-protein are unmeasurable, a ≥ 50% decrease in the difference between involved and uninvolved FLC levels is required in place of the M-protein criteria.
 
If serum and urine M-protein and serum FLC are unmeasurable,² then ≥ 50% reduction in plasma cells is required in place of M-protein, provided baseline bone marrow plasma cell percentage was ≥ 30%
 
In addition to the above listed criteria, if present at baseline, a ≥ 50% reduction in the size of soft tissue plasmacytomas is also required

SD	Not meeting criteria for CR, VGPR, PR, MR or PD
PD	
Progressive Disease requires any one or more of the following:
 
Increase of ≥ 25% from baseline in:
 
 --- serum M-component and /or (the absolute increase must be ≥ 0.5 g/dL) --- urine M-component and/or (the absolute increase must be ≥ 200 mg/24 h) 
Only in subjects without measurable serum and urine M-protein levels: the difference between involved and uninvolved FLC levels. The absolute increase must be > 10 mg/dL.
 
Bone marrow plasma cell percentage: the absolute % must be ≥ 10%
 
Definite development of new bone lesions or soft tissue plasmacytomas or definite increase in the size of existing bone lesions or soft tissue plasmacytomas
 
Development of hypercalcaemia (corrected serum calcium > 11.5 mg/dL or 2.65 mmol/L) that can be attributed solely to the plasma cell proliferative disorder

Source: Durie BG, Harousseau JL, Miguel JS, Bladé J, Barlogie B, Anderson K, et al. International uniform response criteria for multiple myeloma. Leukemia 2006 Sep;20(9): 1467–73. Errata in: Leukemia 2006 Dec;20(12):2220. Leukemia 2007 May;21(5):1134.

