7.7.2 Progression Free Survival (PFS)

PFS is defined as number of days between start of treatment and first evidence of documented disease progression or death (due to any cause), whichever occurs first. Disease progression will be determined by the local investigator for regimens with the same baseline using the International Uniform Response Criteria ([Durie et al. 2006, with corrections](#)) (IMWG-URC) for multiple myeloma subjects and RECIST criteria ([Therasse et al. 2000](#)) for solid tumor subjects. PFS will be re-calculated whenever the baseline is reset due to addition of new anti-cancer therapy or increase of carfilzomib dose/frequency:

- 1) For regimens that continue from initial study without baseline being reset, if subjects didn't progress before PX-171-010, then PFS for the period from initial study to PX-171-010 study will be calculated as Disease Progression /Death Date – Date of first dose in initial study + 1 day, and PFS for the period of PX-171-010 study only will be calculated as Disease Progression /Death Date – Date of first dose in PX-171-010 + 1 day.
- 2) For regimens that start in PX-171-010 study with baseline being reset from initial study or previous regimens, PFS will be calculated as Disease Progression /Death Date –

Date of first dose in the first regimen among the regimens with common baseline + 1 day.

PFS will be right-censored for subjects who met one of the following conditions: 1) no baseline disease assessments or any post-baseline assessments, 2) alive and does not have documentation of disease progression before a data analysis cutoff date. The PFS censoring rules are described in Table 1.

Table 1. Censoring Rules for PFS Analysis

Situation	Date of Progression or Censoring	Outcome
No baseline disease assessments or any post-baseline assessments	Date of first dose	Censored
Alive and without documentation of disease progression	Date of last disease assessment	Censored
Death or disease progression between planned disease assessments	Date of death or first disease assessment showing disease progression, whichever occurs first	Progressed
Death or PD immediately after more than 1 consecutively missed disease assessment visit*	Date of last disease assessment before the first missed visit	Censored
Death before first disease assessment	Date of death	Progressed

* If death or PD is more than 168 days after previous disease assessment, or the first dosing date if there is no previous disease assessment.

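### The myeloma hypercalcaemia criterion pairs two calcium limits that differ by about 8% (11.5 mg/dL is 2.87 mmol/L, not 2.65 mmol/L)

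*Protocol*

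**What the plan says.** The PD row of Protocol Appendix D gives the calcium criterion as "Development of hypercalcaemia (corrected serum calcium > 11.5 mg/dL or 2.65 mmol/L", for a rise "that can be attributed solely to the plasma cell proliferative disorder". No other criterion has to be met at the same time: "Progressive Disease requires any one or more of the following".

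The table feeds the efficacy analysis directly. Protocol 10.4.2 says "The date of progression will be determined using the progression criteria described in" Appendices D and E. Under SAP 7.7.2, "Disease progression will be determined by the local investigator", and SAP 7.7 bases all efficacy analyses on the investigator's assessment as entered on the CRF. For myeloma, SAP 7.7.2 names the published international uniform response criteria, with their corrections, and does not refer to Appendix D. Protocol 7.8 has subjects assessed by the methods of their previous carfilzomib study.

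Protocol 3.2 places the sites as follows: "Approximately 50 study centers in the United States (US) and Canada". Neither document gives the units in which site laboratories report calcium, a conversion factor, a rule on which unit governs, or the calcium limit at any other place.

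**The concern.** A limit printed in two units should describe one level. If it does not, the same blood result can be classified in two ways, and the unit on the laboratory report decides which. Any one criterion is enough for PD, and neither document describes a central review for myeloma, so a discrepant call would pass into the data as recorded.

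At stake are PD dates in the myeloma cohort. PD is an event for both PFS and TTP. SAP 7.7.1 gives OS as a listing without Kaplan-Meier estimates, so PFS and TTP are the only secondary endpoints estimated by that method.

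Reading the word between the two figures as a true alternative does not help. Every calcium above 11.5 mg/dL also exceeds 2.65 mmol/L, so if either limit were enough, the mg/dL figure would never operate.

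**Working it through.** **Inputs**
- Limit in mg/dL: 11.5 (Protocol Appendix D, PD row).
- Limit in mmol/L: 2.65 (same line).
- Molar mass of calcium: 40.08 g/mol. This is a physical constant that the documents do not give.

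**Formula.** mmol/L = (mg/dL × 10) / molar mass, and mg/dL = mmol/L × molar mass / 10.

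**Trying to reproduce the printed 2.65 mmol/L from 11.5 mg/dL**
- 11.5 × 10 / 40.08 = 2.869, or 2.87 mmol/L. The printed figure is not reproduced.
- In reverse, 2.65 × 40.08 / 10 = 10.62 mg/dL.
- Gap: 11.5 − 10.62 = 0.88 mg/dL, or 2.87 − 2.65 = 0.22 mmol/L.
- Ratio: 2.869 / 2.65 = 1.083, so the mg/dL limit is 8.3% higher than the mmol/L limit.

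**Can rounding or the choice of constant explain it?**
- Values that round to 11.5 mg/dL (11.45 to 11.55) convert to 2.857 to 2.882 mmol/L.
- Values that round to 2.65 mmol/L (2.645 to 2.655) convert to 10.60 to 10.64 mg/dL.
- The two ranges do not overlap.
- With a molar mass of 40.0, or the rounded factors 0.25 or 0.2495, 11.5 mg/dL is still 2.869 to 2.875 mmol/L.
- For the two limits to agree, the molar mass would have to be 115 / 2.65 = 43.4 g/mol.

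**What the gap does to one result.** A corrected calcium of 11.0 mg/dL is 110 / 40.08 = 2.74 mmol/L. It exceeds 2.65 mmol/L but not 11.5 mg/dL. The same holds for every value above 10.62 and up to 11.5 mg/dL (above 2.65 and up to 2.87 mmol/L).

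**What cannot be computed.** The documents give neither the share of sites reporting in mmol/L nor how often calcium alone is the first sign of PD, so no count of affected subjects follows.

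**The case against.** The other side accepts the arithmetic and disputes what follows from it. There are five arguments.

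- **Units.** Nothing in the documents says that any site reports calcium in mmol/L. The other serum concentration limits in Appendix D (M-protein in g/dL, free light chains in mg/dL) and the creatinine in the Protocol 6.2.3.1 formula are in conventional units only. This stands. Reporting in mmol/L is an assumption, made plausible by the Canadian sites and by the printing of a second unit. A reader might infer that PD is in fact called early at some sites, or that PFS varies by country. The documents do not support that.
- **Treatment.** A reader might infer that a calcium value in the gap would by itself end treatment. Protocol 3.4 requires confirmed progression and discussion with the Medical Monitor, so that inference fails. The discussion may catch some discrepant calls, but it does not ensure that the recorded PD date rests on one limit.
- **Source.** Appendix D is presented as taken from a published standard, and the mismatch may have been inherited. That cannot be checked here. Wherever it came from, the two figures still disagree inside this protocol, and Protocol 10.4.2 relies on them.
- **A new number could do harm.** Assessments follow parent-study methods. Where the baseline is not reset, one of the PFS and TTP calculations runs from the first dose in the initial study. A limit changed only in this protocol could put two limits inside one interval. This stands, and it shapes the fix.
- **Reach.** The issue concerns the myeloma cohort only, calcium as the first qualifying sign, values within the gap, and sole attribution to the disease. The primary endpoint is safety, and Protocol 10.1 tests no hypotheses. This stands and sets the weight of the point.

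**Conclusion.** The inconsistency is real. The two limits differ by 0.88 mg/dL (0.22 mmol/L), rounding does not account for it, and nothing elsewhere in either document resolves it. It falls on a criterion that can establish PD alone, so it should be corrected and not left as a typographical matter.

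The consequence is conditional. If at least one site reports in mmol/L and applies the limit printed in that unit, a myeloma subject with a corrected calcium above 10.62 and up to 11.5 mg/dL, attributed solely to myeloma, may be recorded as progressed there and not at a site reporting in mg/dL. That could move some PD dates in PFS and TTP. The number cannot be derived. Given how many conditions must coincide, it is probably small, though that is a judgement and not a calculation. Severity is minor.

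**What to change.** Reconcile the two figures against the parent protocols and the published criterion that SAP 7.7.2 cites. Then state one governing limit, or one governing unit, in both Appendix D and SAP 7.7.2. Which level governs is for the sponsor to settle from those sources; the conversions above show only that the figures disagree.

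Apply the chosen limit uniformly across the initial-study and PX-171-010 parts of each PFS and TTP interval, so that no interval is judged by two limits.

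Before PFS and TTP are derived, identify PD calls that rest on calcium alone and check each against the limit. The database may not allow this by itself, because chemistry results are not routinely recorded on CRFs (Protocol Section 7 and Appendix A, footnote 6). Protocol Section 8 requires source documentation of progression, so a targeted site query is feasible.

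The cost is a correction to one line of Appendix D, a sentence in SAP 7.7.2, and a site query whose size is unknown until those PD calls are counted. A few PD dates may move.

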7.9 CORRELATIVE STUDIES

7.9.1 CYTOGENETIC AND FISH STUDIES

A bone marrow biopsy and/or aspirate for determining percent plasma cell involvement, including metaphase cytogenetic and FISH studies are optional for all MM subjects entering with a PR, MR, or SD. Samples for cytogenetic and FISH analysis will also be optional for all MM subjects who discontinue study due to PD. Bone marrow cytogenetic and FISH analyses will be carried out at the site's local laboratory, per standard of practice, or in a Central Reference Laboratory.

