¹ Presence/absence of clonal cells is based upon the κ/λ ratio. An abnormal κ/λ ratio by immunohistochemistry and/or immunofluorescence requires a minimum of 100 plasma cells for analysis. An abnormal ratio reflecting presence of an abnormal clone is κ/λ of > 4:1 or < 1:2.

² Measurable disease: serum M protein ≥ 1 g/dL, urine M-protein > 200 mg/24 h, or serum involved FLC levels > 10 mg/dL with a normal κ/λ ratio.

All response categories require 2 consecutive assessments made at any time before the institution of any new therapy; all categories also require no known evidence of progressive or new bone lesions if radiographic studies were performed. Radiographic studies are not required to satisfy these response requirements.

Minimal Response	
Response Subcategory	Response Criteria
MR	
25%–49% reduction in the level of serum M-protein or a 50%–89% reduction in 24 hours urinary M-protein, which still exceeds 200 mg/24 h, maintained for a minimum of 6 weeks.
 
For subjects with non-secretory myeloma only, 25%–49% reduction in plasma cells in a bone marrow aspirate and on trephine biopsy, if biopsy is performed, maintained for a minimum of 6 weeks.
 
25%–49% reduction in the size of soft tissue plasmacytomas (by radiography or clinical examination)

Source: Bladé J, Samson D, Reece D, Apperley J, Björkstrand B, Gahrton G, et al. Criteria for evaluating disease response and progression in subjects with multiple myeloma treated by high-dose therapy and haemopoietic stem cell transplantation. Myeloma Subcommittee of the EBMT. European Group for Blood and Marrow Transplant. Br J Haematol 1998 Sep; 102(5):1115–23.

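### Appendix D footnote 2 ties FLC-measurable myeloma to a normal kappa/lambda ratio, which conflicts with the rest of the appendix and can misroute the partial-response rule for subjects followed only by FLC

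*Protocol*

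**What the plan says.** Footnote 2 of Protocol Appendix D gives three alternative ways for myeloma to be measurable: serum M-protein, urine M-protein, or FLC. The FLC limb is "or serum involved FLC levels > 10 mg/dL with a normal" kappa/lambda ratio.

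Elsewhere the same appendix says:

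- **sCR row:** "CR as defined below plus normal FLC ratio and absence of clonal cells in bone marrow by immunohistochemistry or immunofluorescence".
- **Footnote 1**, on marrow plasma cells: "An abnormal ratio reflecting presence of an abnormal clone is κ/λ of > 4:1 or < 1:2".
- **PR row, second rule**, for unmeasurable serum and urine M-protein: "a ≥ 50% decrease in the difference between involved and uninvolved FLC levels is required in place of the M-protein criteria".
- **PR row, third rule**, the only place that carries the footnote 2 mark. It begins "If serum and urine M-protein and serum FLC are unmeasurable" and then requires a reduction of at least 50% in plasma cells, provided the baseline marrow percentage was at least 30%.
- **PD row:** for subjects without measurable M-protein, progression by FLC is also scored on the involved-minus-uninvolved difference.

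Protocol Section 7.9.1 says that marrow samples, including those for percent plasma cells, "are optional for all MM subjects entering with a PR, MR, or SD". Sections 7.1 and 7.7 also mark them optional. SAP Section 7.7.4.1 counts sCR, CR, VGPR and PR towards the objective response rate (ORR) in the myeloma cohort.

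**The concern.** A measurability rule should pick out subjects who have enough abnormal protein for a change to be seen. Footnote 2 does the reverse for FLC. It admits subjects whose ratio is normal and shuts out those whose ratio shows an imbalance.

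The footnote is attached to an operative rule, the choice between a blood-based and a marrow-based test for PR. A subject who should be followed by FLC can be sent to a plasma-cell criterion for which the study may hold no data. A real PR might then go unrecorded. ORR could be lowered if the subject counts as a non-responder. If the subject is dropped as missing, the denominator changes instead.

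**Working it through.** The plan derives no figure from this definition, so the check is mainly one of logic, with one small identity.

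**1. What the FLC rules need.** Let I be involved FLC, U uninvolved FLC and r = I/U. The quantity scored in the PR and PD rows is

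D = I − U = I × (1 − 1/r).

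At the footnote's threshold, I = 10 mg/dL:

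- r = 1: D = 10 × (1 − 1) = 0 mg/dL. A 50% decrease has nothing to act on.
- The documents give no normal range for the serum ratio. Borrowing footnote 1's marrow limits purely as an assumption:
  - kappa involved, r at most 4: D is at most 10 × (1 − 1/4) = 7.5 mg/dL;
  - lambda involved, r at most 2: D is at most 10 × (1 − 1/2) = 5 mg/dL.

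D scales with I, so these are values at the threshold only. They show the direction: the closer the ratio is to balance, the less there is to measure.

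**2. Two subjects under the literal text.** Both have serum M-protein below 1 g/dL, urine M-protein not above 200 mg/24 h, and involved FLC above 10 mg/dL.

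| | Abnormal ratio | Normal ratio |
|---|---|---|
| FLC-measurable under footnote 2? | No | Yes |
| FLC-ratio condition of sCR met at baseline? | No | Yes |
| Sign of a clone, by footnote 1's reasoning? | Yes | No |
| Third PR rule (plasma cells) triggered? | Yes | No |

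The first subject has the imbalance that the FLC rules were written for, and is the one the footnote excludes.

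**3. Whether the marrow rule can be applied.** The third PR rule needs a baseline plasma-cell percentage of at least 30% and a later value. Appendix A schedules study marrow samples only at screening and end of study. Section 7.1 offers the screening sample to myeloma subjects in PR, MR or SD. Section 7.7 ties the end-of-study sample to discontinuation for PD. All are optional. The study's own samples are therefore not set up to document a PR; that would depend on marrow taken under the prior protocol's methods.

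**4. Where it can reach the analysis.** SAP Section 5.5 normally keeps the initial study's baseline. It resets the baseline for subjects who enter after progression or other anti-cancer therapy, and again when agents are added during PX-171-010. SAP Section 7.7.4.1 judges best response for regimens that share a baseline. At a new baseline, the initial study's measurable-disease category no longer settles the matter.

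**5. Where it does not clearly reach.** The second PR rule and the FLC route to PD depend on unmeasurable M-protein. Neither carries footnote 2 nor states an FLC-measurability condition.

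**The case against.** The best case on the other side is that this is a probable wording slip with little reach. Much of that stands.

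- **Other methods govern.** Protocol Section 7.8 has assessments follow the prior study. SAP Section 7.3 takes the measurable-disease category from the initial study, and SAP Section 7.7.4.1 cites the published criteria directly. This narrows the effect but does not remove it: Protocol Sections 5, 7.1, 7.6, 7.7 and 7.8 all send the assessor to Appendices D–E, and investigators make the assessments.
- **The routing is not forced.** For the subject with an abnormal ratio, the second PR rule also applies on its own terms, so an investigator can use the FLC difference and never consult footnote 2. That is right. The literal text then supports two PR rules at once, which is itself a reason to reconcile it.
- **Marrow may be available anyway.** Extent-of-disease measurements by the prior protocol's method remain required and might include marrow. The parent protocols are not in the documents, so this stays open.
- **A PDF-reading artefact.** It cannot be fully excluded. But turning *an abnormal* into *a normal* would need letters lost from two adjacent words, and the result reads as grammatical text.

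A reader might infer that every light-chain subject is affected. The documents do not support that: the limbs of footnote 2 are alternatives, so urine M-protein above 200 mg/24 h makes a subject measurable whatever the ratio. A reader might also infer that meeting footnote 2 amounts to sCR. It does not, because sCR also requires CR and absence of clonal marrow cells.

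**Conclusion.** The inconsistency is real and can be shown from Appendix D alone. No other section corrects it, and the amendment summary lists no change to it. It can misstate best response and ORR for myeloma subjects who have neither measurable serum nor measurable urine M-protein, mainly where the baseline is reset within PX-171-010. This assumes that at least some assessors apply the footnote as written.

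The consequence is limited. ORR is an additional analysis in the SAP, the protocol tests no hypothesis, and the primary endpoints are safety endpoints that do not use this definition.

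Three further readings go beyond the documents:

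- **PFS and TTP are compromised.** Not shown, because the FLC route to PD states no FLC-measurability condition.
- **A count of affected subjects.** The documents give about 100 subjects in total (Protocol Section 10.5), but neither the size of the myeloma cohort nor the share followed only by FLC. All that follows is that one misclassified subject among n in the denominator shifts ORR by 100/n percentage points.
- **Response category at entry is wrong.** Not demonstrated, since assessment at entry follows the prior study's method.

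**What to change.** Reconcile footnote 2 with the sCR row, footnote 1 and the FLC-difference rules. The appendix's own logic points to an abnormal kappa/lambda ratio as the intended condition; the sponsor should confirm this against the published criteria that Appendix D cites before changing the text. The urine threshold in the same footnote should be left alone in this edit, because the documents do not show that its inequality sign is wrong.

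The cost is about one word in Appendix D. It needs no new data collection and no change to the planned analyses.
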